4.4.6. Indirect Ophthalmoscopy

Indirect ophthalmoscopy will be performed to assess retinal and choroid appearances and vitreous haze (Nussenblatt et al. 1985). Indirect ophthalmoscopy will be performed for study eye and fellow eye with pupil dilation and should be conducted after IOP measurement has been completed.

Abnormal indirect ophthalmoscopy results for the study eye and fellow eye will be summarized by visit through week 24 and 52 separately.

4.4.7. Prior and Concomitant Medications

Prior and concomitant medications for both ocular and non-ocular indications will be coded using the World Health Organization (WHO) Drug Dictionary. These medications (prescription, OTC, and nutritional supplements) will be summarized by anatomical therapeutic chemical (ATC) classification level 2 term, WHO generic name, and treatment group. Subjects will only be counted once at each level of the generic name or ATC level.

4.4.7.1. Use of Rescue and Prohibited Medications

All prohibited medications used concurrently (from Day 1 through Month 12) must be documented in the eCRF. During the study, some subjects may require rescue treatments in the study eye as a result of AEs or lack of efficacy of the study treatment. Prior to database lock, the Sponsor will conduct a data review to classify concomitant treatments as either rescue or prohibited. The proportion of subjects receiving these medications will be summarized by treatment type (rescue or prohibited), treatment group, and time point.

4.4.8. Clinical Laboratory Evaluation

Clinical laboratory results of hematology, chemistry, and urinalysis will be presented by treatment group using descriptive statistics. For hematology, shift tables of the worst on-study laboratory toxicity based on CTCAE grading relative to baseline will be presented. Subject incidence tables of grade ≥ 3 laboratory toxicities will be provided for hematology and chemistry.

Laboratory values will be listed by subject, and values outside of a normal reference range will be flagged.

4.4.9. Vital Signs, Physical Findings and Other Observations Related to Safety

Observed and change from baseline for each vital sign parameter will be summarized descriptively by treatment group.

4.5. Interim Analysis

No formal interim analyses are planned for this study.

4.6. Primary Analysis

Not applicable.

4.7. Final Analysis

The final analysis will be performed at the end of study when all subjects have completed the week 52 visit or terminate early from the study.

4.8. Changes to Protocol-planned Analyses

There are modifications from the clinical study protocol amendment (protocol version 3.0, 20 July 2022) that impact statistical analysis.

- Hypothesis testing using the exact binomial test will not be conducted to test the difference between the proportion of subjects with a recurrence using a 2-sided alpha = 0.05 due to insufficient sample size. Instead, the number and proportion of subjects who experience the uveitis recurrence will be summarized by treatment group.
- Analysis populations are defined to include subjects who are randomized for the study.

5. Sample Size Determination

A total of approximately 60 subjects will be enrolled in the study and receive either Yutiq 0.05 mg or a sham injection. The Sponsor decided to stop enrollment for reasons other than safety or efficacy, following FDA advice received on January 24, 2022. In early May 2022, subject enrollment into the study has been stopped; therefore, the sample size will represent the number of subjects enrolled at the time of the Sponsors decision to stop enrollment.

6. Supporting Documentation

6.1. Appendix 1: List of Abbreviations

Abbreviation / Acronym	Definition / Expansion
AE	Adverse event
ATC	Anatomical Therapeutic Chemical
BCVA	Best corrected visual acuity
BMI	Body Mass Index
CI	Confidence interval
CRF	Case Report Form
CTCAE	Common Terminology Criteria for Adverse Events
EDTRS	Early Treatment Diabetic Retinopathy Study
FA	Fluocinolone acetonide
IOP	Intraocular pressure
ITT	Intent-to-treat
IVRS	Interactive Voice Response System
MedDRA	Medical Dictionary for Regulatory Activities
OTC	Over-the-counter
PD	Protocol deviation
PT	Preferred Term
SAE	Serious adverse event
SAP	Statistical Analysis Plan
SD-OCT	Spectral-domain Optical Coherence Tomography
SOC	System Organ Class
TEAE	Treatment-emergent adverse event
WHO-DD	World Health Organization - Drug Dictionary

6.2. Appendix 2: Supporting Study Information

6.2.1. Disposition of Subjects

A summary table will be prepared indicating the number and percentage of subjects in each treatment group who are included in each analysis population. Within the ITT population, the number and percentage of subjects who did/did not complete the study will be presented. Screen failures, including reasons for failing to satisfy eligibility criteria will also be summarized. In addition, randomization stratification and subgroups will be summarized.

Subjects who discontinue any time during the study will be summarized by reason for termination. Duration of study participation and insert duration will also be tabulated.

6.2.2. Demographics

Demographics and baseline characteristics data include age (in years, at time of signing informed consent) and age category (< 65 vs \geq 65), race, sex, childbearing potential, ethnicity, height, weight, calculated BMI, and geographic region, and will be summarized by treatment group using descriptive statistics for the ITT population.

6.2.3. Baseline and Disease Characteristics

Optical baseline characteristics include dilated indirect ophthalmoscopy results, baseline BCVA group (\leq 64 vs $>$ 64 letters), BCVA ETDRS letter score, intraocular pressure, ocular tolerability, and anterior, posterior and intermediate slit lamp examinations, and SD-OCT, and will be summarized by treatment group using descriptive statistics with the ITT analysis set.

6.2.4. Protocol Deviations

Protocol Deviations (PDs) data will be identified and recorded. The study team will conduct ongoing reviews of the PD data throughout the study. A summary of incidence of major PDs will be tabulated using number and percentage of subjects by deviation type.

Listings of subjects with PDs will be provided.

6.2.5. Medical History and Concurrent Illnesses

Medical history data including ophthalmic history will be coded using the MedDRA version 24.1 or higher and summarized by SOC and PT for each treatment group.

6.2.6. Prior/Concomitant Medications

Prior medications are defined as all prescription, vaccinations, supplements, herbal therapies, any

prohibited medications, and over-the-counter (OTC) medications taken within the 30 days to day 1 whether subjects continue to take or not. All prior medications must be documented on the concomitant medications eCRF.

Concomitant Medications are all prescription and OTC concomitant medications used concurrently from the time of ICF signing through Month 12 and documented on the concomitant medication eCRF.

Information on the concomitant medication/therapy eCRF includes the name of the medication/therapy, dose, frequency, route, dates of use, and indication for use.

Prior and concomitant medications will be coded using the World Health Organization-Drug Dictionary (WHO-DD) version September 2021 B3 and will be summarized by preferred name.

The number and percentage of subjects using each medication will be presented by treatment group using the safety analysis set. Subjects taking more than one medication in the same preferred name will be counted once for the number of subjects taking that preferred name.

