3.3 Duration of Study

All subjects who were randomized to Yutiq 0.05 mg will be followed for 12 months after treatment on a modified protocol schedule. Subjects who were randomized to the sham injection have been discontinued from the study and underwent their EOS visit. After the initial Screening

visit, subjects will have up to 30 days to be enrolled. Study treatment will be administered on Day 1. Eligible subjects who are enrolled in this study and randomized to receive Yutiq 0.05 mg will be seen for 8 scheduled study visits over approximately 12-14 months depending on the time between initial Screening, Day 1, and the final study visit at Month 12. Screen failures will be recorded along with the reason(s) for not meeting the eligibility criteria.

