7 CONCOMITANT MEDICATIONS/PROCEDURES

7.1 Prior Medications

Prior medications are defined as all prescription, vaccinations, supplements, herbal therapies, any prohibited medications, and over-the-counter (OTC) medications taken within the 30 days (whether continuing or not) prior to Day 1. All prior medications must be documented on the concomitant medications eCRF.

7.2 Tapering/Ending Systemic or Topical Uveitis Treatment Following Day 1

Subjects may be treated prior to entry in order to meet study inclusion criteria. The objective of prior treatment is to obtain a relatively quiet eye prior to enrollment. If a subject is receiving systemic corticosteroids or immunosuppressants, or topical steroids to control uveitis prior to study enrollment, that subject will have such treatment ended within 3 months following Day 1, in a manner that follows the standard of care for ending the specific treatment. For example, some systemic treatment regimens may be ended immediately, while others require a period of gradual dose reduction (tapering). Systemic medications or topical steroids administered as part of gradual dose reduction are not considered prohibited medications.

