7.5 Concomitant Medications

All prescription and OTC concomitant medications used concurrently (from the time of ICF signing through Month 12) must be documented on the concomitant medication eCRF.

Information on the concomitant medication/therapy eCRF includes the name of the medication/therapy, dose, frequency, route, dates of use, and indication for use. Subjects should be instructed not to take any medication including OTC products, without first consulting with the Investigator. Any AE(s) that result(s) from taking a concomitant medication/therapy following the first study dose should be recorded on the AE eCRF.

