6.3. Appendix 3: Data Handling Conventions

6.3.1. Missing Date Imputation

6.3.1.1. Missing/Incomplete AE and Medication Start Date

For AEs and Prior/Concomitant medications, the following imputation rules will be applied to impute partial or missing start dates.

- If year, month, and day are all missing, then assign the date of study drug administration.
- If month and day are missing and year is:
 - the same as the year of study drug administration then assign the month-day of study drug administration
 - earlier than the year of study drug administration then assign December 31
 - after the year of study drug administration then assign January 1.
- If only day is missing, and month-year is:
 - the same as the month-year of study drug administration then assign the day of study drug administration
 - earlier than the month-year of study drug administration then assign the last day of the month
 - after the month-year of study drug administration then assign the first day of the month.

If the imputed start date is after the stop date, then there is a data error and do not impute the start date.

The imputed dates will be used to assess whether AEs should be considered as treatment emergent and if medications should be included in the safety summaries as prior or concomitant. The original, partial dates will be included in data listings.

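### SAP 6.2.6 counts concomitant medication from consent rather than from injection, and the start-date rule in 6.3.1.1 labels some valid pre-injection records as errors

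*SAP*

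**What the plan says.** **Definitions.** SAP 6.2.6 says: "Concomitant Medications are all prescription and OTC concomitant medications used concurrently from the time of ICF signing through Month 12". The same section defines prior use as "medications taken within the 30 days to day 1 whether subjects continue to take or not". Both kinds are recorded on one eCRF page, so a record's category has to come from its dates. The consent start follows Protocol 7.5, which is an instruction on recording: medications in use "from the time of ICF signing through Month 12) must be documented on the concomitant medication eCRF".

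**Tabulation.** "The number and percentage of subjects using each medication will be presented by treatment group using the safety analysis set" (SAP 6.2.6). SAP 4.4.7 adds a summary by ATC level 2, generic name and arm. Neither section cuts at injection or asks for separate prior and concomitant tables.

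**Time between consent and injection.** After the first Screening "visit, subjects will have up to 30 days to be enrolled" (Protocol 3.3). Treatment in this period is expected: "The objective of prior treatment is to obtain a relatively quiet eye prior to enrollment" (Protocol 7.2).

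**Date rule.** SAP 6.3.1.1 covers AEs and medications and is anchored to study drug administration. For example: "If year, month, and day are all missing, then assign the date of study drug administration". It then adds: "If the imputed start date is after the stop date, then there is a data error and do not impute the start date". It says the imputed dates decide treatment-emergent status and whether a medication is prior or concomitant.

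**The concern.** A collection window has become an analysis definition. Recording medication from consent is sound. Using consent as the cut between prior and concomitant leaves two overlapping categories with no tie-break. It also conflicts with 6.3.1.1, where the reference point is the injection and the consent date plays no part. Two programmers could derive different flags from the same data. Use of concomitant medication is a listed safety item (SAP 1.1), and a course that ended before the subject was randomized says nothing about what was needed after treatment.

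The date rule is a second, independent problem. It pushes an incomplete start as late as the injection or the end of the recorded month. It then treats the conflict it has created with a known stop as evidence of bad data. Protocol 8.3 collects AEs from consent, so screening-period AEs are exposed in the same way as medications.

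**Working it through.** **Overlap.** Let consent fall c days before Day 1, with c from 0 to 30 (Protocol 3.3; I assume consent is signed at the Screening visit). Prior covers the 30 days before Day 1. Concomitant covers consent to Month 12. The overlap before injection is min(c, 30) = c days, so 0 to 30 days. Three cases follow for a medication taken before Day 1:

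- Stopped before consent: prior only.
- Taken only between consent and Day 1: meets both definitions. This is the defect.
- Continued past Day 1 (for example an entry regimen being tapered): concomitant under either cut, and rightly so.

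**Date rule.** I applied 6.3.1.1 literally, with an assumed injection on 15 Mar 2022:

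| Recorded start | Recorded stop | Imputed start | Result |
|---|---|---|---|
| 2022 only | 20 Feb 2022 | 15 Mar 2022 | after stop: called an error |
| Mar 2022, day missing | 12 Mar 2022 | 15 Mar 2022 | after stop: called an error |
| Feb 2022, day missing | 26 Feb 2022 | 28 Feb 2022 | after stop: called an error |
| Fully missing | 12 Mar 2022 | 15 Mar 2022 | after stop: called an error |
| Feb 2022, day missing | 12 Mar 2022 | 28 Feb 2022 | accepted |

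All five records can be genuine.

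**Which records can be hit.** If the true start is on or before injection, the imputed date is never later than injection. If the true start is after injection, the imputed date is never later than the true start. A valid record whose stop is on or after injection therefore cannot fail the check. Only courses or events that ended before injection can.

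**Enumeration as a check on the logic.** Assumed injection dates run from 1 Nov 2021 to 5 May 2022 (186 days). For each date I took every course with start no later than stop in the preceding 30 days: 30 × 31 / 2 = 465 courses, and 186 × 465 = 86,490 in all. Called errors:

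- Day missing: 56,324 / 86,490 = 65.1%.
- Month and day missing: 81,530 / 86,490 = 94.3%.
- Fully missing: 86,490 / 86,490 = 100%.

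A control set of courses starting 0 to 30 days after injection and lasting 0 to 30 days (186 × 31 × 31 = 178,746) gave 0 errors for every type of missing date. These percentages come from a uniform grid. They show which side of injection is affected and do not estimate how often it will happen.

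**After the fix.** With imputed start = min(rule date, recorded stop), 0 of the 86,490 are called errors. With concomitant defined as a stop on or after injection, or ongoing use, 0 of the 86,490 count as concomitant.

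**The case against.** The strongest reply is that the use that matters is reported elsewhere. SAP 4.4.7.1 classifies treatments as rescue or prohibited and summarizes them by arm and time point, with prohibited use documented from Day 1. Treatment given to quiet the eye and stopped before Day 1 is neither. This stands and removes most of the consequence. The general tables still carry tapering and post-surgical topical steroid, which Protocol 7.7 does not count as prohibited.

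A reader might infer that pre-injection steroid would hide a treatment effect on steroid need. The documents do not support that:

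- They give no share of subjects treated only between consent and Day 1.
- Peri-ocular steroid within 12 weeks before Day 1 is an exclusion (Protocol 4.2), and entry regimens may run up to 3 months past Day 1 (Protocol 7.2), so the affected group may be small.
- The SAP specifies no pooled steroid row.
- Use before randomization blurs a comparison but does not systematically favor an arm.
- Sham subjects were discontinued in early May 2022 while Yutiq subjects continue to Month 12, so follow-up differs by arm under any definition.
- Recurrence, vitreous haze and BCVA summaries remain (SAP 4.2 and 4.3).

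A reader might also infer that an AE caught by the date rule has no treatment-emergent status. That too goes further than the text. The stop date is kept and the original partial dates are listed. Under SAP 4.4.2 an event that ended before injection can neither have started nor worsened after it. What is missing is a sentence telling the program to use the stop date.

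Finally, the consent window matches Protocol 7.5, all analyses are descriptive, and all data are listed by subject (SAP 4.1.1). These points limit the harm but do not resolve the overlap or correct the date rule.

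**Conclusion.** Both gaps are real on the text, and both are minor. Under SAP 6.2.6, a drug taken only between consent and injection is prior and concomitant at once, and it enters the by-arm tables with no cut at injection. Under 6.3.1.1, a valid course or AE that ended before injection can be labelled an error solely because its start date is incomplete.

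The first affects at most the 30 days before Day 1. The second affects only records with a partial or missing start and a stop earlier than the imputed date; fully dated records are untouched. The documents give neither the number of subjects treated only in that period nor the number of partial dates, so no effect on any table can be computed. The rescue/prohibited summary is largely unaffected, and the efficacy endpoint summaries do not use either rule. The conclusion rests on reading both sections literally, with recorded stop dates taken as correct.

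**What to change.** **SAP 6.2.6.** Define concomitant as any use on or after the Day 1 injection (active or sham), including use that began earlier and continued. Put medications stopped before injection in the prior category only. Tabulate the two separately, and carry the same split into 4.4.7. Collection from consent stays as it is.

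**SAP 6.3.1.1.** Set the imputed start to the earlier of the rule-based date and the recorded stop date. Keep the error label for real conflicts, where the recorded year or month of the start is already later than that of the stop. State that an AE whose stop date precedes injection is not treatment-emergent.

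I would not add a rule that dates a drug by the visit at which it was first entered, because the eCRF content listed in 6.2.6 shows no such field.

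**Cost.** A few sentences and a small change to the derivation program. No new data and no change to conduct. If the database is already locked, SAP section 1 allows the change to be documented in the clinical study report.

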6.3. Appendix 3: Data Handling Conventions

6.3.1. Missing Date Imputation

6.3.1.1. Missing/Incomplete AE and Medication Start Date

For AEs and Prior/Concomitant medications, the following imputation rules will be applied to impute partial or missing start dates.

- If year, month, and day are all missing, then assign the date of study drug administration.
- If month and day are missing and year is:
 - the same as the year of study drug administration then assign the month-day of study drug administration
 - earlier than the year of study drug administration then assign December 31
 - after the year of study drug administration then assign January 1.
- If only day is missing, and month-year is:
 - the same as the month-year of study drug administration then assign the day of study drug administration
 - earlier than the month-year of study drug administration then assign the last day of the month
 - after the month-year of study drug administration then assign the first day of the month.

If the imputed start date is after the stop date, then there is a data error and do not impute the start date.

The imputed dates will be used to assess whether AEs should be considered as treatment emergent and if medications should be included in the safety summaries as prior or concomitant. The original, partial dates will be included in data listings.

6.3.1.2. Missing/Incomplete AE and Medication End Date

Imputation rules for partial or missing stop dates

- if day is missing, assign the last day of the month.
- if month-day is missing, assign December 31 of the year.
- if year, month, and day are all missing, do not impute.

If the stop date imputation leads to a date that is after the death date, then impute the stop date as the death date.

If the stop date imputation leads to a date that is before the start date, then there is a data error and do not impute the stop date.

